Hereby, patients of the control arm shall receive serial cervical length measurements by transvaginal ultrasound (TVS) every 4 weeks started at 12+0 weeks.

A cerclage may be indicated when the cervical length is below 25 mm.¹ (s. consort-diagram).

Sample size:

For sample size calculation, we assume a combined event rate for the primary outcome (long-term survival without neurodevelopmental disability at 3 years of follow up) of 8% for the pessary group and an event rate of 20% for the control group van't Hooft 2016. Group sample size of 121 in both groups achieve 80% power to detect this difference using a two-sided chi-square test with significance level alpha=5%. To account for a drop out rate around 25%, sample size of 155 in each group, overall n=310 women will be recruited.

Study calendar:

Starting recruitment: June, 1st, 2018

Finishing recruitment and follow-up: est. June 1st, 2023.

Final report: Sept. 1st, 2023.

Table of contents

1. General Information

- 1.1. Title, protocol identifying number and date.
- 1.2. Name and address of the Sponsor.
- 1.3. Name and title of the authorized person by the Sponsor to sign the protocol and the protocol amendments.
- 1.4. Name, title, addresses and telephone numbers of the medical experts of the Sponsor of the trial.
- 1.5. Name and title of all the researchers who are responsible for conducting the trial and address and telephone numbers of trial sites.
- 1.6. Name, title, address and telephone number of the qualified physician who is responsible for all medical decisions on each trial site.
- 1.7. Name and address of the medical departments or institutions that are involved in the trial.

2. Rationale

- 2.1. Justification of the relevance of the trial.
- 2.2. Description of the study population.
- 2.3. Name and description of the device under investigation.
- 2.4. Statement that testing will be performed according to the protocol, GCP and applicable legal requirements.

3. Objective

4. Design

- 4.1. Specific description of primary and secondary variables.
 - 4.1.1. Primary outcome.
 - 4.1.2. Secondary outcomes.
- 4.2. Description of the trial design.

Confidential

- 4.3. Flowchart.
- 4.4. Description of the medical device and treatment regimen.
- 4.5. Expected duration of subject's participation.
- 4.6. Completion and interruption criteria of the study or the subjects.
- 4.7. Maintenance of the randomization codes and test procedures of the trial.

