(2) The primary outcome will be evaluated 3 years after the last woman enrolled in this study has delivered her neonate.

Confidential

A descriptive analysis by preterm birth will be carried out calculating means and medians for quantitative variables and proportions with 95% confidence intervals for categorical variables.

Additionally we will perform an explorative subgroup analysis of the study collective comparing the efficacy of the cervical pessary treatment in women with a normal cervical length at 12 -16 weeks of gestation and in women who have developed a cervical shortening (< 25 mm) as an additional risk factor.

For the primary endpoint we expect to have a drop out rate of up to 25% due to the long follow-up time (3 years) of the study; but we do not expect to have lost data for the secondary endpoints because for these parameters the study has a short follow-up time till time to birth only.

An interim analysis shall be conducted on key safety parameters after birth of 150 neonates: the following safety endpoints will be assessed by a one-sided test with $\alpha=1\%$

- on level of the neonates:

rate of preterm birth, time to birth, birth weight, death, neonatal morbidity, harm of intervention

- and on the maternal level:

rate of hospitalisation for threatened preterm labour < 32 weeks, rate of P_{RoM} <32 weeks, rate of infection / inflammation, rate of physical or psychological intolerance to pessary, rate of SAR/SAE, death.

The trial will be terminated as negative if a disadvantage for the pessary-treatment can be found in one of these tests. To guarantee a high safety level the significance level is chosen more conservatively than in a Bonferroni correction. All analysis will be carried out with SPSS® version 19.0 or later (IBM Company SPSS Inc.

Headquarters, Chicago, Illinois, USA) and R version 3.2.3 or later (R Foundation for Statistical Computing, Vienna, Austria).

Primary Outcome	Statistical Test
Children`s Long-Term Survival without Neurodevelopmental Disability (3-Years-follow up)	Chi-Square test
Secondary Outcome	Statistical Test
Birth before 34 Weeks of Gestation	Chi-Square test or Fisher test
Time to Birth	Cox regression
Birthweight	t-test or Wilcoxon-Mann-Whitney test
Fetal / Neonatal Death	Chi-Square test or Fisher test
Neonatal Morbidity	Chi-Square test or Fisher test
Need for Hospitalization	Chi-Square test or Fisher test
Days of Hospitalization	t-test or Wilcoxon-Mann-Whitney test

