Maternal Adverse Events	Chi-Square test or Fisher test
Pessary Intolerance	Chi-Square test or Fisher test
Vaginal Infections	Chi-Square test or Fisher test

9.2. Expected number of subjects to be included.

For sample size calculation, we assume a combined event rate for the primary outcome (long-term survival without neurodevelopmental disability at 3 years of follow up) of 8% for the pessary group (see van't Hooft, Pro Twin Trial²⁸) and an event rate of 20% for the control group. Group sample size of 121 in both groups achieve 80% power to detect this difference using a two-sided chi-square test with significance level $\alpha=5\%$. To account for a drop out rate around 15%, sample size of 155 in each group, overall n=310 women will be recruited.

9.3. Criteria for termination of the trial.

A non-justified case of maternal death (temporary stop until complete evaluation of the case by an external committee).

9.4. Selection of subjects to be included in each analysis.

The analysis will include all the subjects that have been randomised.

10. Direct Access to Data Source

Direct access will be granted to the authorized monitor, host institution and the regulatory authorities to permit trial-related monitoring, audits and inspections.

11. Quality and Control Assurance

Main investigator and collaborators: In order to ensure the Quality of the data they will provide instructions and training to the sites involved in the trial; review the CRF data; and detail of any other steps taken to ensure quality of research.

The main investigator will sign the study protocol and the “investigator’s commitment; he will apply for the Ethics Committee and the Director’s approval; and he will review the final report of the study.

The collaborators will assess patient’s eligibility, they will inform the patients and ask for the informed consent; and they will be responsible of the CRF and obtaining and registering all data.

Monitor: he will perform regular monitoring according to ICH GCP. Data will be evaluated for compliance with the protocol and accuracy in relation to source documents. Monitors will verify that the clinical trial is conducted and data are generated, documented and reported in compliance with the protocol, GCP and the applicable and local regulatory requirements.

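### The sample-size figures do not fit together: 121 per arm falls short of 80% power, dropout is given as both 25% and 15%, and 310 women at 25% loss give about 75% power

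*Combined protocol and SAP*

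**What the plan says.** The sample-size paragraph appears twice, in the synopsis (Sample size) and in section 9.2. Both versions assume "of 8% for the pessary group" and "an event rate of 20% for the control group", and both state: "Group sample size of 121 in both groups achieve 80% power to detect this difference using a two-sided chi-square test", at a 5% significance level. Both then arrive at 155 per arm and 310 in total.

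They differ in the dropout rate that is meant to explain the step from 121 to 155:

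- Synopsis: "To account for a drop out rate around 25%, sample size of 155 in each group, overall n=310 women will be recruited".
- Section 9.2: "To account for a drop out rate around 15%, sample size of 155 in each group, overall n=310 women will be recruited".

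Section 9.1 sides with the synopsis: "For the primary endpoint we expect to have a drop out rate of up to 25" per cent, which it puts down to the three-year follow-up.

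Both versions also attach the planning rates to the favourable outcome: "long-term survival without neurodevelopmental disability at 3 years of follow up) of 8% for the pessary group".

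**The concern.** One recruitment target is justified by two different dropout rates, so at least one passage is wrong. The evaluable number per arm also looks too small for the stated power, and 155 does not follow from it at either rate. A reader cannot tell how many evaluable children the trial needs, or whether 310 women will supply them at the loss the plan itself anticipates.

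The labelling adds a second difficulty. Taken literally, the plan assumes that the pessary lowers disability-free survival from 20% to 8%, which is the opposite of the benefit set out in section 3. Section 9.1 promises relative risks, and their value and direction depend on which event is counted.

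**Working it through.** **Inputs.** p1 = 0.08 (pessary), p2 = 0.20 (control), difference 0.12, two-sided alpha 5%, 80% power, 155 per arm (synopsis and section 9.2). Chi-square as the primary test (section 9.1). Dropout 25% (synopsis), up to 25% (section 9.1), 15% (section 9.2).

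**Step 1: trying to reproduce 121.** The pooled-variance formula for two proportions, with mean rate 0.14, is

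n = [1.960·√(2·0.14·0.86) + 0.842·√(0.08·0.92 + 0.20·0.80)]² / 0.12²

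= [1.960·0.4907 + 0.842·0.4833]² / 0.0144 = 130.07, so 131 per arm.

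Other two-sided methods give:

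| Method | n per arm for 80% power |
|---|---|
| Pooled formula | 131 |
| Unpooled formula (127.3) | 128 |
| Arcsine (125.4) | 126 |
| Exact enumeration, uncorrected chi-square | 128 (power 80.2%) |
| Continuity-corrected | 147 |

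None gives 121. The only nearby value is 119, from a one-sided continuity-corrected formula, and that contradicts the stated two-sided test.

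**Step 2: trying to reproduce 155.** Enrolment is N = n/(1 − dropout), rounded up.

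| Evaluable n | 15% loss | 25% loss |
|---|---|---|
| 121 | 142.4, so 143 | 161.3, so 162 |
| 131 | 154.1, so **155** | 174.7, so 175 |

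Multiplying instead of dividing does not help: 121 × 1.25 = 151.25, so 152. Going from 121 to 155 implies a loss of 1 − 121/155 = 21.9%, a rate given nowhere. Of these combinations, only 131 with 15% loss returns 155.

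**Step 3: power at the numbers that would be available.** With n per arm, power = Φ([0.12·√n − 1.960·0.4907] / 0.4833). At 25% loss, 155 × 0.75 = 116.25, so 116. At 15% loss, 155 × 0.85 = 131.75, so 131.

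| Evaluable per arm | Pooled formula | Exact enumeration, uncorrected chi-square |
|---|---|---|
| 116 (155 at 25% loss) | 75.3% | 76.4% |
| 121 (as stated) | 77.1% | 78.4% |
| 131 (155 at 15% loss) | 80.3% | 81.2% |

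For 116, for example: (0.12·10.770 − 0.9618)/0.4833 = 0.684, and Φ(0.684) = 0.753. With a continuity correction or Fisher's test, power at 116 is about 69 to 70%.

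**Step 4: the event label.** Reversing the event to 92% versus 80% leaves n at 131, so the label does not affect power. It does affect the relative risk: 0.08/0.20 = 0.40 for death or disability, but 0.92/0.80 = 1.15 for disability-free survival.

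**The case against.** Several points can be made for the plan.

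- **The required number depends on the formula.** Exact enumeration of the named test reaches 80% at 128, and arcsine gives 126. This is fair, but every two-sided method tried exceeds 121.
- **The shortfall at 121 is small.** It is 2.9 points by the pooled formula (80 − 77.1), 1.6 by exact enumeration of the chi-square (80 − 78.4), and only 0.8 by enumeration of the likelihood-ratio version (79.2%). This stands: on its own, the 121 would be a minor correction.
- **Section 9.1 gives 25% as a ceiling.** That is so, and the power statement should be worded accordingly. But the synopsis uses about 25% as the planning value itself, so power at 25% is the plan's own case.
- **That 121 is a slip for 131 is an inference.** The documents show no calculation behind either number. The inference fits section 9.2 exactly, but the finding does not depend on it.
- **The intended direction is clear.** The objective and the words about event rates make it plain that 8% and 20% are unfavourable outcomes, and the test is two-sided. This is a labelling error and adds nothing to the power argument. It still needs correcting because of the relative risks.

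None of this removes the conflict between 15% and 25%, or the shortfall at 25% loss.

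**Conclusion.** The concern holds. The synopsis and section 9.2 contradict each other on dropout, the stated 121 per arm is below what 80% power requires (131 by the pooled formula, 128 by exact enumeration), and 155 follows from 121 at neither stated rate. If loss reaches 25%, 310 women give about 75 to 76% power, so the risk of missing the assumed effect is about 24 to 25% instead of 20%. The target of 310 delivers 80% only if loss stays at about 15%.

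These figures take the plan's 8% and 20% as given. They assume equal loss in both arms, no outcome for children lost to follow-up, and an uncorrected chi-square test. The power deficit is moderate. It must be fixed because it concerns the sample-size basis of the primary endpoint and the plan contradicts itself there.

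**What to change.** 1. Re-derive the evaluable number and name the formula. With the pooled formula, replace 121 by 131 per arm in the synopsis and section 9.2.
2. Use one dropout figure in the synopsis, section 9.1 and section 9.2.
3. Relabel the planning event and use the same event for the relative risk.

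Wording that keeps N unchanged:

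*Planning event: death or neurodevelopmental disability by 3 years, 8% in the pessary group and 20% in the control group (disability-free survival 92% and 80%). With a two-sided chi-square test at 5%, 131 evaluable children per group give 80% power. Recruiting 310 women gives 80% power if loss is at most 15%, and about 75% power if loss reaches 25%.*

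The cost is a change of text and a slightly less favourable power statement, with no extra patients. If the sponsor prefers to keep 80% power at 25% loss, the target becomes 131/0.75 = 175 per arm, or 350 women, which is 40 more than planned (171 per arm if 128 from exact enumeration is used). Either choice is defensible, provided the text says which was made.

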13.1. Data ownership

Sponsor and participating Center have expressly agreed that any and all data collected and prepared in the context of the study shall be the property of the Sponsor, provided that participating Center shall remain the owner of its source data and may utilize such data as it deems appropriate without the approval, but with the reliable communication of Sponsor. Furthermore, Sponsor will always have access to the Study data, in terms of good faith and cooperation, in order to improve their own knowledge and information.

14. Funds and Insurance

According to German legislation and Ethical Committee decisions, it is not necessary to enter into an insurance contract in order to cover patients while using this medical device in a clinical trial. Insofar as it has been issued with the appropriate certificate of the State Medicines Agency to the concrete use of the medical device.

Nevertheless, it will be mandatory to enter into a hedging insurance by any other participating centre of this clinical trial, in the case that it is mandatory according to the laws of their country.

No funding is provided for the study.

15. Publication policy

The Sponsor takes the commitment of publishing the results of the study; despite they are good or bad.

Promoter and participating Centre agree that publications or presentations of any of the results from the study shall be in accordance with accepted scientific practice, academic standards and customs.

Confidential

Authorship and other related publications questions shall be addressed in accordance with the principles of the 'Uniform Requirements for Manuscripts Submitted to Biomedical Journals' and in accordance with the requirements of the respective medical journal.

Sponsor agrees to ensure co-authorship for clinical co-investigators on any proposed multicentre publication.

Sponsor and participating Centres agree that at first they will strive to make a joint publication. After such joint publication or one year after termination of the study the following shall be agreed:

Annex I. Technical details of the device.

The Arabin cervical pessary

CE-certified for preventing spontaneous preterm birth (CE 0482 / EN ISO 13485: 2012 + AC:2012 annex III of the council directive 93/42 EEC).

This pessary is used to treat pregnant women with cervical incompetence in order to support the cervix and sacralise it towards the sacrum.

It may be indicated in pregnancies with a history of premature labour, multiple pregnancies or mothers who are exposed to physical strain (e.g. standing for a long time). It may also be indicated in pregnant women suffering from prolapse of the genital organs.

The cerclage pessary can easily be folded and inserted without pain.

In general, cerclage pessaries should have a height of 21-25 mm in singleton pregnancies and a height of 25-30 mm in multiple pregnancies or pregnant patients with complaints of prolapse. The width of the upper and lower diameter should be chosen depending on the individual constitution of the pregnant patient.

Cerclage pessaries can be ordered in a non-perforated or perforated version. The perforations facilitate discharge to pass.

Sizes and Models: Cerclage pessaries are classified according to

- The lower larger diameter (65 or 70 mm)
- The height (17, 21, 25, 30 mm)
- The upper smaller diameter (32 or 35 mm)

[name] online shop. <http://www.dr-arabin.de/e/cerclage.html>
